### Secondary Objective

To assess the change in neurocognitive function and brain MRI progression over the course of PER treatment with a daily dose of 4 mg (up to -8mg) in patients with biopsy-proven high-grade glioma and focal epilepsy compared with alternate ASDs.

To identify a biomarker-specific response to seizure-reduction in patients treated with PER in patients with a biopsy-proven high-grade glioma (i.e., IDH-mutant vs wildtype).

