#### **4.3 Subject Recruitment, Enrollment and Screening**

Subjects (n = 20), will be male and female adults with a high-grade glioma recruited from Mayo Clinic in Jacksonville, Florida- [name], DO, (PI). 10 subjects will be enrolled into an adjunctive Perampanel and other ASDs group, and 10 subjects will receive only alternative ASDs. There will be a 6-month recruitment period for screening and enrollment. The treating physician will decide, based on best medical practice, which patients are candidates for adjunctive Perampanel and other ASDs, or only alternative ASDs. Patients taking Perampanel will begin their titration phase upon enrollment.

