#### Handling of Missing Data

Study data will be collected and managed using REDCap electronic data capture tools hosted at Mayo Clinic. All data requested on the Case Report Form (CRF) will be recorded for each participant. A standardized CRF will be generated by REDCap. For any data query, the Principal Investigator and Investigators will meet to clarify the data queried and make corrections based on consensus. Once the study is completed, the Principal Investigator will randomly select 3 participants and compare the data documented for each on the CRF with what is entered into the REDCap database. If there is any discrepancy, the Principal Investigator and/or Investigators will cross-reference all 20 patients to ensure accuracy.

**Primary Hypothesis:** We hypothesize that perampanel will lead to a significant reduction in seizure frequency for adult patients with brain tumor-related seizures associated with high-grade glioma.

We will compare seizure frequency before and 3 months after treatment with monotherapy and adjunctive PER and use descriptive statistics to demonstrate differences in responders. A P-value < 0.05 will be used to reflect statistical significance.

**Secondary Hypothesis 1:** We hypothesize the progression of brain tumor (comparing 4 and 8 mg/d of perampanel) based upon fusion by comparing baseline brain MRI and MRI at 12 months will be less for IDH-mutants.

We hypothesize there will be minimal or no change in neurocognitive function from 0 to 3 months on Montreal Outcome Cognitive Assessment (MOCA; higher scores indicating greater function); and the Clinical Global Impression of Change (CGIC; scores from 1 to 7, with lower scores indicating greater improvement and a score of 4 indicating no change).

Chi-square and Student T-test will be used to measure differences in assessment and change during the study period. A P-value < 0.05 will be considered significant.

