Actual Lethality/Medical Damage: 0. No physical damage or very minor physical damage (e.g., surface scratches). 1. Minor physical damage (e.g., lethargic speech; first-degree burns; mild bleeding, sprains). 2. Moderate physical damage; medical attention needed (e.g., conscious but sleepy, somewhat responsive; second-degree burns; bleeding of major vessel). 3. Moderately severe physical damage; medical hospitalization and likely intensive care required (e.g., comatose with reflexes intact; third-degree burns less than 20% of body; extensive blood loss but can recover; major fractures). 4. Severe physical damage; medical hospitalization with intensive care required (e.g., comatose without reflexes; third-degree burns over 20% of body; extensive blood loss with unstable vital signs; major damage to a vital area). 5. Death		Enter Code	Enter Code	Enter Code	
Potential Lethality: Only Answer if Actual Lethality=0 Likely lethality of actual attempt if no medical damage (the following examples, while having no actual medical damage, had potential for very serious lethality: put gun in mouth and pulled the trigger but gun fails to fire so no medical damage; laying on train tracks with oncoming train but pulled away before run over).		Enter Code	Enter Code	Enter Code	
0 = Behavior not likely to result in injury 1 = Behavior likely to result in injury but not likely to cause death 2 = Behavior likely to result in death despite available medical care					

**Assessment 4: MOCA.** Score  $\geq 26$  is normal; scores  $<26$  indicate mild cognitive impairment and possible dementia

MONTREAL COGNITIVE ASSESSMENT (MOCA)						NAME : _____	Education : _____	Date of birth : _____	Sex : _____	DATE : _____	
VISUOSPATIAL / EXECUTIVE 						Copy cube	Draw CLOCK (Ten past eleven) (3 points)				POINTS _____/5
						[ ]	[ ] Contour	[ ] Numbers	[ ] Hands		
NAMING 						[ ]	[ ]	[ ]	[ ]	_____/3	
MEMORY Read list of words, subject must repeat them. Do 2 trials. Do a recall after 5 minutes.						FACE	VELVET	CHURCH	DAISY	RED	No points
1st trial _____ 2nd trial _____											
ATTENTION Read list of digits (1 digit/ sec.). Subject has to repeat them in the forward order Subject has to repeat them in the backward order						[ ] 2 1 8 5 4	[ ] 7 4 2	_____/2			
Read list of letters. The subject must tap with his hand at each letter A. No points if $\geq 2$ errors [ ] F B A C M N A A J K L B A F A K D E A A A J A M O F A A B								_____/1			

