### Assessment 5: Clinician's Global Impression of Change

**TABLE 2. CGI-I guidelines**

1	= Very much improved—nearly all better; good level of functioning; minimal symptoms; represents a very substantial change
2	= Much improved—notably better with significant reduction of symptoms; increase in the level of functioning but some symptoms remain
3	= Minimally improved—slightly better with little or no clinically meaningful reduction of symptoms. Represents very little change in basic clinical status, level of care, or functional capacity
4	= No change—symptoms remain essentially unchanged
5	= Minimally worse—slightly worse but may not be clinically meaningful; may represent very little change in basic clinical status or functional capacity
6	= Much worse—clinically significant increase in symptoms and diminished functioning
7	= Very much worse—severe exacerbation of symptoms and loss of functioning

Adapted from Spearing MK, Post RM, Leverich GS, et al. Modification of the Clinical Global Impressions (CGI) Scale for use in bipolar illness (BP). *Psychiatry Res* 1997;73(3):159–71.

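### The little-or-no-change hypothesis for MOCA and CGIC at 3 months is tied only to difference tests at P<0.05, which cannot support it, and no MOCA change margin or interval rule is given

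*Combined protocol and SAP*

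**What the plan says.** The hypothesis is in Section 7.2, in the text under Handling of Missing Data: "We hypothesize there will be minimal or no change in neurocognitive function from 0 to 3 months on Montreal Outcome Cognitive Assessment". The sentence goes on to CGIC, where a score of 4 means no change. The analysis follows: "Chi-square and Student T-test will be used to measure differences in assessment and change during the study period", with P<0.05 counted as significant. The Study Summary and the opening of 7.2 name the same two tests and no others.

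Other parts of the protocol that bear on this:

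- **Objective.** Section 2 lists as secondary: "To assess the change in neurocognitive function and brain MRI progression over the course of PER treatment", compared with alternate ASDs.
- **MOCA.** The only threshold is in Section 15, Assessment 4, where scores below 26 "indicate mild cognitive impairment and possible dementia". That cut-off describes status at one visit, not change.
- **CGIC.** Section 15, Assessment 5 does anchor the scale. A rating of 5 is "slightly worse but may not be clinically meaningful", and a rating of 6 is "clinically significant increase in symptoms and diminished functioning". Section 7.2 does not say how ratings will be summarised for a group.
- **Size and allocation.** Section 4.3: "10 subjects will be enrolled into an adjunctive Perampanel and other ASDs group, and 10 subjects will receive only alternative ASDs". Also: "The treating physician will decide, based on best medical practice, which patients are candidates for adjunctive Perampanel and other ASDs".
- **Analysis set.** Section 3.4 calls for intent to treat and, for subjects who die before 12 months, the latest data before death. Section 7.3 analyses the protocol-compliant population. Under Section 5.3, PER subjects must tolerate 4 mg to continue.
- **Time point.** Section 3.4 also lists neuropsychological decline at 6 months, under the primary endpoints.

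**The concern.** The hypothesis and the test point in opposite directions. The hypothesis is that little or nothing changes, but a t-test or chi-square for a difference can only gather evidence that something did change. A significant result counts against the hypothesis, or says nothing about it if the shift is trivial. A non-significant result may mean no change, or too few subjects to see it. The plan offers no other criterion, so the reading of a non-significant result would be chosen after the data are seen.

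The pilot is meant to inform a larger multi-center trial (Section 7.1). A report of no significant cognitive change, without an interval, would tell the planners of that trial little about cognitive safety and could reassure them wrongly.

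**Working it through.** **Logic.** The core of the point needs no numbers. Failing to reject a null of no change does not establish it, whatever the SD. The arithmetic shows only how much change could go unseen here. The plan's N of 20 is a feasibility target with no power inputs, so there is no figure to reproduce.

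**Inputs.** From the documents: 10 per arm (4.3) and alpha 0.05 (7.2). Assumed: two-sided tests, no dropout (the best case) and normal change scores. The plan does not say whether change is tested within the PER arm or between arms, so both are shown.

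**Step 1. Largest observed mean decline that is still non-significant, in SDs of change.**

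- Paired, n = 10: t(0.975, 9)/√10 = 2.262/3.162 = 0.72 SD.
- Between arms, 10 v 10: t(0.975, 18) × √(2/10) = 2.101 × 0.447 = 0.94 SD.
- If only 8 per arm were evaluable (assumed): 2.365/√8 = 0.84 SD and 2.145 × √(2/8) = 1.07 SD.

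**Step 2. Chance of missing a true decline of 0.5 SD (noncentral t).**

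- Paired: noncentrality 0.5 × √10 = 1.581, 9 df. P(non-significant) = 0.707.
- Between arms: noncentrality 0.5/√(2/10) = 1.118, 18 df. P(non-significant) = 0.815.

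**Step 3. In MOCA points.** The SD of change is not in the documents, so 2, 3 and 4 points are assumed. Chance of missing a true 2-point decline:

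| Assumed SD | Paired, PER arm | Between arms |
|---|---|---|
| 2 | 20% | 44% |
| 3 | 53% | 71% |
| 4 | 71% | 81% |

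**Step 4. What a margin rule would deliver.** Chance that the whole interval for the PER-arm mean change (n = 10) lies inside the margin when true change is zero. The margins are illustrative.

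| Margin, interval | SD 2 | SD 3 | SD 4 |
|---|---|---|---|
| ±2 points, 90% CI | 80% | 28% | 7% |
| ±2 points, 95% CI | 61% | 12% | 2% |
| ±3 points, 90% CI | 99% | 80% | 43% |
| ±3 points, 95% CI | 97% | 61% | 23% |

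The 90% interval corresponds to the usual two one-sided 0.05 tests, and the 95% interval is stricter. Between arms at ±2 points the chances are 39%, 2.7% and 0.1% (90% CI) or 18%, 0.4% and under 0.1% (95% CI).

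**Step 5. CGIC.** If all 10 PER subjects were rated 3 to 5, the exact 95% lower limit would be 0.025^(1/10) = 69%. If none of 10 were rated 6 or 7, the upper limit would be 1 − 0.692 = 31%.

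**The case against.** The strongest reply is that this is a declared feasibility pilot. Section 7.1 says it is not powered for effectiveness, the tests sit under a descriptive-statistics heading, and the Section 2 objective is to assess change, which is estimation. MOCA and CGIC are collected at baseline and Visit 8 (Day 90), so means and intervals can be computed at reporting even if 7.2 is left alone. All of that stands, and it keeps the priority modest. It does not remove the P<0.05 criterion that 7.2 attaches to this hypothesis.

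A reader might infer more than the documents support:

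- **That the sponsor will declare no change from P>=0.05.** The plan does not say so. The fault is that it gives no other criterion.
- **That minimal change is undefined throughout.** For CGIC, ratings 3 to 5 are anchored. The missing margin concerns MOCA. The CGIC anchors describe global symptoms and functioning, so they cannot stand in for cognition either.
- **That a 2-point MOCA decline would usually be missed.** That depends on the SD. At an assumed SD of 2 the paired test has about 80% power.
- **That the study cannot answer the question or must be enlarged.** The limit lies in the stated criterion, not in the data collected. The sample size is a feasibility choice.
- **That a margin rule is bound to be inconclusive.** Step 4 shows that this turns on the SD, the margin and the interval level.

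**Conclusion.** The point holds. The hypothesis of little or no change has no criterion in the plan that could support it, and no MOCA change margin or interval rule appears anywhere in the documents. That conclusion rests on the text alone.

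Its size in SD units (declines of up to 0.72 or 0.94 SD non-significant; a true 0.5 SD decline missed in 71% or 81% of trials) rests on 10 evaluable subjects per arm, two-sided tests and normal change scores. Ten is the ceiling, because deaths, intolerance and withdrawal can only lower it. Everything in MOCA points rests on assumed SDs and should be read as a range. The change is worth making because it is cheap, not because the trial fails without it.

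**What to change.** In Section 7.2, replace the P<0.05 criterion for this hypothesis with estimation:

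1. Report the mean MOCA change from baseline to Day 90 in the PER arm and the baseline-adjusted difference between arms, each with a 95% CI. Label the between-arm estimate descriptive, because the treating physician chooses the arm.
2. State that P>=0.05 is not evidence of no change.
3. Report the Day 90 CGIC distribution by arm, with the proportions rated 3 to 5 and 6 to 7 and exact 95% CIs. Describe it as global change, not cognition.
4. Report by arm how many subjects have no Day 90 score and why (death, not tolerating 4 mg, withdrawal), and limit any statement to those assessed. Reconcile the analysis set between Section 3.4 (intent to treat, latest data before death) and Section 7.3 (protocol-compliant).
5. Report the 6-month neuropsychological endpoint of Section 3.4 in the same way.
6. Only if the sponsor wants to conclude that there was no meaningful change, fix and justify a MOCA margin before analysis, and the interval level with it: 90% for the usual two one-sided 0.05 tests, or the stricter 95%.

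**Cost.** A few sentences, with no new visits, instruments or subjects. The downside is that a margin-based conclusion may well be inconclusive at this size, depending on the SD, margin and interval level.

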## 7 Statistical Plan

### 7.1 Sample Size Determination

A sample size of 20 patients is targeted as part of a pilot study to determine feasibility for a larger prospective multi-center trial. The sample size is targeted to achieve adequate enrollment and determine the likelihood of supporting a larger study.

This study is not designed to be powered to determine significance for statistical significance of effectiveness.

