### 7.2 Statistical Methods

#### Descriptive Statistics

Statistical analysis will include Student T-test, Chi-square for categorical differences. An interim analysis will be performed when half of subjects are enrolled.

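### Section 7.2 names only chi-square and the Student t-test, judged at P < 0.05, for groups of ten or fewer: it should specify exact tests between groups and paired tests for any within-patient change

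*Combined protocol and SAP*

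**What the plan says.** Section 7.2, under Descriptive Statistics, gives the general method: "Statistical analysis will include Student T-test, Chi-square for categorical differences". The hypotheses appear further on, under the Handling of Missing Data heading. For cognition the plan states "We hypothesize there will be minimal or no change in neurocognitive function from 0 to 3 months", measured by MOCA and CGIC. It then adds "Chi-square and Student T-test will be used to measure differences in assessment and change during the study period", and "A P-value < 0.05 will be considered significant". The same 0.05 threshold is set for the primary hypothesis, which compares seizure frequency before treatment and three months after.

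The groups are small. Section 4.3 states "10 subjects will be enrolled into an adjunctive Perampanel and other ASDs group, and 10 subjects will receive only alternative ASDs", with the treating physician choosing the group. Section 7.3 analyses protocol-compliant patients and ties evaluability at 3, 6 and 12 months to disease severity and risk of death. Section 3.4 makes provision for patients who die before 12 months. The biomarker objective in Section 2 compares IDH-mutant with wildtype tumours among perampanel patients.

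On power, Section 7.1 states "This study is not designed to be powered to determine significance for statistical significance of effectiveness". The documents name no exact test, McNemar test, paired t-test or continuity correction. They give no loss rate, response rate or IDH split.

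**The concern.** There are two separate issues.

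**Sparse tables.** The chi-square P-value is a large-sample approximation. At 10 per arm, the expected count in the rarer category is 10 times the pooled rate, so it is below 5 unless that rate is exactly 50%. With fewer evaluable patients or an uneven IDH split, counts fall further. The true error rate can then depart from 5% in either direction, depending on the table shape, the underlying rate and whether a continuity correction is used. A categorical result could be called significant when an exact test would not support it.

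**Unspecified pairing.** The cognitive hypothesis concerns the same patients at 0 and 3 months. The sentence on tests does not say whether change is assessed within patients or compared between groups. On the within-patient reading, an unpaired chi-square or t-test treats two measurements on one person as independent. The cognitive hypothesis is one of little or no change, so a test that loses sensitivity would lean toward the hoped-for answer.

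**Working it through.** The plan has no power or sample-size figure to reproduce; the only stated figure is the 0.05 level. The check asks what the true level of the named test is.

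**Inputs from the documents:** 10 and 10 patients (4.3); P < 0.05 (7.2); chi-square for categories (7.2); IDH comparison within the perampanel group (2).

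**Assumptions:** two-sided testing; 5 to 10 evaluable patients per arm; every possible IDH split of 10; a common response rate p anywhere between 0 and 1.

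**Step 1: exact size of the uncorrected test.** For responders a of n1 and b of n2, with N = n1 + n2 and s = a + b,

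X² = N [a(n2 − b) − b(n1 − a)]² / [n1 n2 s (N − s)],

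and the test rejects if X² > 3.841. Size at p is the sum, over rejecting tables, of the two binomial probabilities. The maximum is taken over p.

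| Comparison | Maximum size, uncorrected | Average over p | Maximum size, Yates |
|---|---|---|---|
| 10 v 10 (as planned) | 4.2% | 2.8% | 1.3% |
| 9 v 9 | 5.7% | 3.6% | 1.0% |
| 8 v 8 | 7.7% | 3.9% | 2.1% |
| 9 v 7 | 8.1% | 5.2% | 1.6% |
| IDH 5:5 | 6.2% | 4.0% | 0.2% |
| IDH 6:4 | 5.1% | 2.4% | 0.2% |
| IDH 7:3 | 6.2% | 3.5% | 0.2% |
| IDH 8:2 | 8.7% | 5.3% | 0.7% |
| IDH 9:1 | 9.0% | 5.5% | 0.0% |

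Over all 21 combinations of 5 to 10 evaluable patients per arm, the uncorrected maximum exceeds 5% in 16. Of those, 14 lie between 5.3% and 6.8%; the other two are 8 v 8 and 9 v 7. Only 9 v 7 passes 8%, for p of about 0.43 to 0.57. The 8:2 split passes 8% only for p of about 0.08 to 0.17, or the mirror range.

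**Step 2: one table.** Take a 7:3 IDH split with responders 3/3 v 2/7.

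- Uncorrected: X² = 10 × (3 × 5 − 2 × 0)² / (3 × 7 × 5 × 5) = 2250 / 525 = 4.29, P = 0.038.
- Yates: 10 × (15 − 5)² / 525 = 1.90, P = 0.17.
- Boschloo: P = 0.07. Barnard: P = 0.06.

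The same data are significant or not depending on which version of chi-square is run, and neither exact unconditional test reaches 0.05.

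**Step 3: the within-patient reading.** For 10 patients measured twice, with no true change and category rates of 0.3 or 0.5, the size of the unpaired chi-square is:

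| Within-patient correlation | Size |
|---|---|
| 0 | 3.7-4.2% |
| 0.3 | 1.4-1.6% |
| 0.5 | 0.5% |
| 0.7 | below 0.1% |

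For power, assume 30% impaired at baseline and half of the rest becoming impaired:

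| Patients | Recovery among impaired | Unpaired chi-square | McNemar mid-P |
|---|---|---|---|
| 20 (both arms pooled) | 0% | 62% | 88% |
| 20 (both arms pooled) | 20% | 43% | 53% |
| 10 (one arm) | 0% | 26% | 25% |

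**The case against.** **Inflation.** A reader might infer from the 8-9% figures that chi-square runs at that error rate in this trial. The documents do not support this. The figures are maxima over an unknown rate in selected splits. Averaged over p, the size in the affected splits is about 3.5-5.5%, and at the planned 10 v 10 there is no inflation. The plan also does not say that the test is uncorrected; with Yates the problem is the reverse. This objection stands as a limit on size. It does not rescue the method, because the plan leaves open two versions that behave very differently.

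**Pairing.** A reader might infer that the plan assigns chi-square to before-after comparisons. The wording equally fits change compared between groups. CGIC is already a rating of change, so comparing its categories between arms is an independent-samples analysis. The plan nowhere proposes testing MOCA above or below 26 before and after; the cut-off appears only in the appendix description of the instrument. What stands is that the test is unspecified.

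**Direction.** It is also tempting to link the pairing issue to the inflated error rates. Ignoring positive pairing lowers the error rate, so the two issues pull in opposite directions.

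**Consequence.** This is a feasibility pilot, responder differences are to be shown with descriptive statistics, and allocation is by physician choice, so confounding matters more than a few points of test size. That is fair and keeps the point modest, but the 0.05 criterion is still applied.

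**Conclusion.** The point holds in a limited form. Section 7.2 commits to chi-square as the only categorical test, at P < 0.05, in samples where its level is unreliable. With complete data at 10 v 10 it is acceptable (at most 4.2%). With losses or an uneven IDH split, the uncorrected test typically has a maximum level of 5-7%, and 8-9% only in the worst cases. A corrected test would be very conservative, at about 2% or less. All of this rests on assumed evaluable numbers, IDH splits and response rates, since the documents give none.

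On change over time, the finding is one of omission: pairing is not specified. If change is tested within patients, unpaired tests are conservative under positive pairing and can lose power. A large power gain from pairing should not be inferred. It depends on pooling 20 patients and on how many recover, and it is absent at n = 10 in the case computed.

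The change is worth making because it is nearly free, but its effect on the conclusions of an unpowered, non-randomised pilot is modest.

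**What to change.** In Section 7.2:

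- For categorical comparisons of Group A with Group B, and of IDH-mutant with wildtype, replace chi-square with one named exact unconditional test (Boschloo or Barnard), two-sided, with an exact 95% confidence interval for the difference in proportions.
- State whether each change analysis is within patients or between groups. For any within-patient categorical change, use the McNemar mid-P test with an interval for the paired difference.
- State that before-after t-tests are paired.

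The cost is a few lines of text and standard software, with no extra patients, visits or data. The downside is a somewhat larger P-value for some borderline tables, as in the example above (0.038 becomes about 0.06-0.07). Fisher's test would also hold the level but is more conservative here (maximum size 1.3% at 10 v 10), which is the reason to prefer an unconditional test.
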